7.1.1 Serious adverse events

Information about all serious adverse events will be collected and recorded. To ensure patient safety each serious adverse event must also be reported to Novartis within 24 hours of learning of its occurrence. A serious adverse event is an undesirable sign, symptom or medical condition which:

- is fatal or life-threatening
- results in persistent or significant disability/incapacity
- constitutes a congenital anomaly/birth defect

- requires inpatient hospitalization or prolongation of existing hospitalization, unless hospitalization is for:
 - routine treatment or monitoring of the studied indication, not associated with any deterioration in condition (specify what this includes)
 - elective or pre-planned treatment for a pre-existing condition that is unrelated to the indication under study and has not worsened since the start of study drug
 - treatment on an emergency outpatient basis for an event not fulfilling any of the definitions of a SAE given above and not resulting in hospital admission
 - social reasons and respite care in the absence of any deterioration in the patient's general condition
 - is medically significant, i.e., defined as an event that jeopardizes the patient or may require medical or surgical intervention to prevent one of the outcomes listed above

Lymphopenia is an expected toxicity of this regimen and is not life threatening. Patients are prescribed prophylactic Bactrim and do not receive more than 6 months of treatment with Temozolomide to minimize the effects of this toxicity. Grade 3-4 lymphopenia will not be considered a Serious Adverse Event. Information regarding this toxicity will be collected although reporting of each instance of grade 3-4 lymphopenia will not be required.

7.1.2 Novartis instructions for rapid notification of serious adverse events

The principal investigator has the obligation to report all serious adverse events to the FDA, IRB, and Novartis Pharmaceuticals Clinical Safety and Epidemiology Department (CS&E).

All events reported to the FDA by the investigator are to be filed utilizing the Form FDA 3500A (MedWatch Form).

All events must be reported, by [contact]), to Novartis Pharmaceuticals CS&E Department within 24 hours of learning of it's occurrence. This includes serious, related, labeled (expected) and serious, related, unlabeled (unexpected) adverse experiences. All deaths during treatment or within 30 days following completion of active protocol therapy must be reported within 5 working days.

Any serious adverse event occurring after the patient has provided informed consent and until 4 weeks after the patient has stopped study participation must be reported. This includes the period in which the study protocol interferes with the standard medical treatment given to a patient (e.g. treatment withdrawal during washout period, change in treatment to a fixed dose of concomitant medication).

Serious adverse events occurring more than 4 weeks after study discontinuation need only be reported if a relationship to the Novartis study drug (or therapy) is suspected.

For Comparator Drugs/Secondary Suspects (Concomitant Medications), all serious adverse experiences will be forwarded to the product manufacturer by the investigator.

7.2 Pregnancies

Any pregnancy that occurs during study participation should be reported. To ensure patient safety each pregnancy must also be reported to Novartis within 24 hours of learning of its occurrence. The pregnancy should be followed up to determine outcome, including spontaneous or voluntary termination, details of birth, and the presence or absence of any birth defects, congenital abnormalities or maternal and newborn complications.

7.3 Evaluations

7.3.1 Hematology

Hematology must include hemoglobin, hematocrit, platelets, total white blood cell count (WBC) and differential.

7.3.2 Blood chemistry

Blood chemistry must be performed in a fasting state and include: fasting glucose, sodium, potassium, chloride, bicarbonate, creatinine, blood urea nitrogen, albumin, total protein, SGOT (AST), SGPT (ALT), total bilirubin, alkaline phosphatase, calcium, magnesium, phosphate. Serum lipid profile (triglycerides, total cholesterol, HDL and LDL) will be checked after every two cycles of therapy.

Because accurate serum glucose and lipid measurements are required, patients should be fasting at the time of the blood sampling.

Assessment of secretory proteins will be performed at baseline. All patients will undergo an initial assessment of chromogranin A. Measurement of gastrin, VIP, or other secretory proteins will also be performed depending on tumor type.

7.3.3 Vital signs

Vital sign assessment consists of height (first visit), pulse, blood pressure, respiration rate, temperature and weight. Blood pressure, pulse and respiration rate should be measured on patients after at least 3 minutes in the sitting position

7.3.4 Physical examination

Physical examination will be performed which must comprise a total body examination (general appearance, skin, neck, including thyroid, eyes, ears, nose, throat, lungs, heart, abdomen, back, lymph nodes, extremities and basic nervous system).

Significant findings made after the start of study drug which meet the definition of an Adverse Event must be recorded.

7.3.5 Performance status

Performance status will be assessed using the Eastern Cooperative Oncology Group (ECOG) performance status scale, as follows:

Grade	Performance Status
0	Fully active, able to carry on all pre-disease performance without restriction
1	Restricted in physically strenuous activity but ambulatory and able to carry out work of a light or sedentary nature, e.g., light house work, office work
2	Ambulatory and capable of all selfcare but unable to carry out any work activities. Up and about more than 50% of waking hours
3	Capable of only limited selfcare, confined to bed or chair more than 50% of waking hours
4	Completely disabled. Cannot carry on any selfcare. Totally confined to bed or chair
5	Dead

* As published in Am. J. Clin. Oncol.:

7.3.6 Drug levels and pharmacokinetic assessments

Drug level and pharmacokinetic assessments will not be measured.

8 Protocol amendments, or changes in study conduct

Any change or addition (excluding administrative) to this protocol requires a written protocol amendment that must be reviewed by Novartis and the investigator before implementation. Amendments significantly affecting the safety of subjects, the scope of the investigation or the scientific quality of the study require additional approval by the IRB at each study center. All amendments must be reviewed by the DFCI IRB. A copy of the written approval of the IRB must be provided to Novartis. Examples of amendments requiring such approval are:

1. increases in drug dose or duration of exposure of subjects,
2. significant changes in the study design (e.g. addition or deletion of a control group),
3. increases in the number of invasive procedures,
4. addition or deletions of a test procedure required for monitoring of safety.

These requirements for approval should in no way prevent any immediate action from being taken by the investigator or by Novartis in the interests of preserving the safety of all patients included in the trial. If an immediate change to the protocol is felt to be necessary by the investigator and is implemented for safety reasons Novartis must be notified and the IRB at the center must be informed immediately. Amendments affecting only administrative aspects of the study do not require formal protocol amendments or IRB approval but the IRB must be kept informed of such administrative changes. Examples of administrative changes not requiring formal protocol amendments and IRB approval include:

1. changes in the staff used to monitor trials
2. minor changes in the packaging or labeling of study drug.

9 Data management

9.1 Data collection

The DF/HCC QACT will develop a set of electronic case report forms (eCRFs). These forms are designed to collect data for each study. The CRCs designated at each institution will enter data on the eCRFs, and data will be reviewed by the Overall PI.

10 Statistical methods

10.1 Sample size and power calculation

The study is designed with a total accrual goal of up to 44 patients (up to 12 in Cohorts 1/2 and up to 32 in Cohort 3). If no toxicity is observed in the first two cohorts of patients, a total of 32 patients in Cohort 3 will be treated at the full dose of each drug (RAD001 at the MTD plus temozolomide).

A two-stage design will be employed for the patients treated at the full doses of each drug: 17 patients in the first stage and 15 patients in the second stage. The research plan incorporates anticipated response rate into the early stopping rule. At the end of the first stage of accrual (17 patients) data will be reviewed to decide if the study should be terminated due to inactivity of the treatment. Thus, the design protects patients from inappropriate treatment. The investigators would wish to conclude that the regimen is worthy of further pursuit if the clinical response rate is 20% or greater, and conclude that the regimen is not worthy of pursuit if the response rate is 5% or less (Please refer to Section 1.2). The proposed design is based on the following criteria:

1. In the first stage, 17 patients will be treated
2. If there are 0 responses, the study will be terminated
3. If there are 1 or more responses, the study will proceed to the second stage, accruing an additional 15 patients to a total of 32
4. If the second stage is completed with a total of 3 or more responses, then it will be concluded that the treatment deserves further study
5. Conversely, if the responses total 2 or fewer, then the treatment will not be recommended for further study.

With this design, the probability of terminating the study after 17 patients is 0.42 if the true but unknown response rate is 5%, but 0.02 if the true but unknown response rate is 20%. The study will have overall power of 0.95, and overall type I error of 0.18. Allowing for a 5% rate of ineligibility, the overall accrual goal will be 32 patients.

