Once the first cohort of patients completes the initial 35-day cycle without experiencing a DLT, the second cohort of patients will begin enrollment. The second patient cohort will consist of at least 3 patients who will receive an oral dose of 10 mg of RAD001 administered daily and an oral dose of temozolomide of 150 mg/m² daily for 7 days every other week beginning on Day 1 of RAD001 administration. The patients will be treated for a 28-day Treatment Period and then observed over a 7-day observation period for signs of treatment-emergent toxicity. Patients will not receive treatment with either RAD001 or temozolomide during the 7-day observation period. If patients do not exhibit disease progression or a dose limiting toxicity (DLT), as defined in section 3.3, they will receive subsequent 28-day cycles of treatment without additional 7-day observation periods. Patients in this cohort may be treated simultaneously without requiring previously enrolled patients to complete their first cycle of treatment and observation.

If a DLT is observed in 1 of the first 3 patients, 3 additional patients will be enrolled at that same dose level. If no additional DLT is observed after all patients have completed the first cycle of treatment and observation period, the trial will continue to enroll the third cohort of patients. If additional DLTs are observed, enrollment to the trial will be stopped and the study will be re-evaluated.

If a DLT is observed in 2 or more of the first 3 patients or of the total 6 patients during Cycle 1 of treatment, accrual to the trial will be suspended pending review of the events and revision of the protocol.

3.2.3 Cohort 3

Once the second cohort of patients completes the initial 35-day cycle without experiencing a DLT, the third cohort of patients will begin enrollment. The third patient cohort will consist of 32 patients who will receive an oral dose of the maximum tolerated dose of RAD001 administered daily and an oral dose of temozolomide of 150 mg/m² daily for 7 days every other week beginning on Day 1 of RAD001 administration. The patients will be treated for a 28-day Treatment Period. Patients who complete the initial cycle of therapy without evidence of significant treatment-emergent toxicity or progressive disease may receive additional 28-day cycles of treatment until the appearance of significant treatment-emergent toxicities or disease progression.

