3.3 Definition of dose limiting toxicity (DLT) and maximum tolerated dose (MTD)

Dose limiting toxicity is defined as drug-related toxicity according to the NCI CTCAE v3.0 during the first cycle of treatment leading to the following:

- Grade 3 or higher non-hematologic toxicity (excluding nausea and/or vomiting).
- Grade 3 or higher nausea/vomiting uncontrolled by aggressive antiemetic support.
- Grade 3 or higher neutropenia or thrombocytopenia failing to revert to grade ≤ 2 (level at which cytotoxic treatment is permitted) in three weeks
- Febrile neutropenia
- Inability of the patient to take $> 75\%$ of the planned chemotherapy dose during the treatment period.
- Clinically significant treatment related toxicity

The maximum tolerated dose (MTD) is defined as the highest dose level at which less than 33% of the patients experience a DLT.

If a DLT is observed in 2 or more of the first 3 patients or of the total 6 patients in a dose level during cycle 1 of treatment, that dose level will be considered to be above the maximum tolerated dose (MTD). The dose one level lower will be declared as the MTD, if a DLT is observed in 1 or less patient of the total 6 patients in the dose level. If 2 or more patients have experienced a DLT at the first dose level, the investigator, medical monitor, and Sponsor may discuss to add a dose level at 50% of the first level.

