12.2 Safety Meetings

The DF/HCC Data and Safety Monitoring Committee (DSMC) will review and monitor toxicity and accrual data from this trial. The committee is composed of clinical specialists with experience in oncology and who have no direct relationship with the study. Information that raises any questions about participant safety will be addressed with the Principal Investigator and study team.

The DSMC will meet quarterly and/or more often if required to review toxicity and accrual data. Information to be provided to the committee may include: up-to-date participant accrual; current dose level information; DLT information; all grade 2 or higher unexpected adverse events that have been reported; summary of all deaths occurring within 30 days for Phase I or II protocols; for gene transfer protocols, summary of all deaths while being treated and during active follow-up; any response information; audit results, and a summary provided by the study team. Other information (e.g. scans, laboratory values) will be provided upon request.

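### The 32-patient Cohort 3 has no pre-set cohort-level toxicity boundary, although the 10 mg level can be cleared on 0/3 or 1/6 DLTs, a rule that passes a true 40% DLT rate with probability 0.31

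*Combined protocol and SAP*

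**What the plan says.** **Clearing the dose.** Section 3.3 sets the MTD as the "highest dose level at which less than 33% of the patients experience a DLT" and counts as a DLT "drug-related toxicity according to the NCI CTCAE v3.0 during the first cycle of treatment". In section 3.2.2, "The second patient cohort will consist of at least 3 patients". With no DLT in the first 3, Cohort 3 opens. With 1 in 3, three more are enrolled and Cohort 3 opens if there is no further DLT. Two or more DLTs suspend accrual. These DLT rules are written under Cohorts 1 and 2; section 3.2.3 has none for Cohort 3.

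**Cohort 3.** Section 10.1 treats 17 and then 15 patients. After the first 17, "data will be reviewed to decide if the study should be terminated due to inactivity of the treatment". The rule is to stop on 0 responses. The same paragraph concludes that the design protects patients from inappropriate treatment.

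**Oversight.** Section 12.2: "The DSMC will meet quarterly and/or more often if required to review toxicity and accrual data". The information supplied may include DLTs, but no count or rate is named that would prompt action.

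**Schedule.** Cohorts 1 and 2 have a week off after the first 28 days: "Patients will not receive treatment with either RAD001 or temozolomide during the 7-day observation period". Section 3.2.3 has no such week for Cohort 3: "The patients will be treated for a 28-day Treatment Period. Patients who complete the initial cycle of therapy" without significant toxicity or progression go on to further 28-day cycles.

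**The concern.** A 3-to-6-patient rule is a coarse screen. It says little about whether the true DLT rate lies below the protocol's own 33% limit, so most of the information on that question will come from Cohort 3. Yet once Cohort 3 opens, no pre-set rule compares its DLT count with the limit. The one formal look, at 17 patients, asks only about response, and an active but too toxic regimen would normally pass it. Section 1.5 says the trial starts below the anticipated phase II dose so as not to miss unexpected toxicity. The statistical section does not carry that aim into the cohort where most patients are treated.

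**Working it through.** **1. The plan's own stopping figure.** Cohort 3 stops on 0 responses in 17 (10.1).
- At a 5% response rate: 0.95^17 = 0.418, against the stated 0.42.
- At 20%: 0.80^17 = 0.023, against the stated 0.02.

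Both reproduce. The DLT rate does not enter the rule. If the response rate is 20%, the look stops the trial about 2% of the time however toxic the regimen is.

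**2. Probability that 10 mg passes Cohort 2.** With true DLT rate q and the rule in 3.2.2 (pass on 0/3, or on 1/3 followed by 0/3):

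P(pass) = (1−q)^3 + 3q(1−q)^2 × (1−q)^3 = (1−q)^3 + 3q(1−q)^5

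| True DLT rate q | On 0/3 | On 1/6 | Pass |
|---|---|---|---|
| 33% | 0.301 | 0.134 | 0.43 |
| 40% | 0.216 | 0.093 | 0.31 |
| 50% | 0.125 | 0.047 | 0.17 |
| 60% | 0.064 | 0.018 | 0.08 |

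About 70% of the passes at 33% to 50% rest on three patients (for example 0.216/0.309 = 0.70).

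**3. Allowing for Cohort 1.** The documents give no DLT rate for the 5 mg level. Assuming 10% to 30%, Cohort 1 passes with probability 0.906 to 0.494. The joint pass probability is then 0.28 to 0.15 when the 10 mg rate is 40%, and 0.16 to 0.09 when it is 50%.

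**4. What a pass excludes.** After 0/3 the exact two-sided 95% upper limit for the DLT rate is 1 − 0.025^(1/3) = 71%. After 1/6 it is 64%. Neither excludes a rate above 33%.

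**5. Consequence in Cohort 3.** If all 32 are treated, the expected DLTs are 32 × 0.40 = 12.8 or 32 × 0.50 = 16. No numerical rule responds to either count.

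**6. A possible boundary.** Suspend accrual at ≥4 of 6, ≥7 of 12, ≥9 of 17 or ≥12 of 24 patients with a cycle 1 DLT. Exact binomial recursion over 32 independent patients, with no enrolment while a look is pending, gives:

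| True DLT rate | P(suspend) |
|---|---|
| 20% | 0.02 |
| 25% | 0.05 |
| 30% | 0.11 |
| 32% | 0.145 |
| 33% | 0.165 |
| 40% | 0.35 |
| 50% | 0.69 |
| 60% | 0.92 |

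Mean enrolment at 50% is 17.9 instead of 32. Combined with step 2, the probability that a level passes Cohort 2 and is never flagged falls from 0.31 to 0.309 × (1 − 0.352) = 0.20 at 40%, and from 0.17 to 0.172 × (1 − 0.690) = 0.05 at 50%.

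**7. Schedule, side by side.** Sections 4.4.2 and 4.5.1 put temozolomide on Days 1-7 and 15-21 of each 28-day cycle in every cohort. Days 1-28 are therefore the same for all: 14 temozolomide and 28 RAD001 days. On Days 29-35 Cohorts 1 and 2 take neither drug, while a Cohort 3 patient who continues on schedule starts cycle 2. Later cycles run without a break in all cohorts (3.2.1, 3.2.2).

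**The case against.** The best defence is that a phase II stage run on DSMC judgement, with no numerical toxicity boundary, is a legitimate design choice and contradicts no stated rule. Protection also exists at other levels:
- The DSMC meets quarterly or more often and may see DLT data.
- SAEs go to the manufacturer within 24 hours (7.1.1, 7.1.2).
- Section 8 allows immediate safety action without waiting for an amendment.
- Sections 4.3 and 4.4 require individual doses to be held, reduced or stopped. Section 4.4.3 and the RAD001 reduction tables name only Cohorts 1 and 2, but 4.4.4 is general.

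All of this stands. It narrows the gap to the missing cohort-level trigger; it does not close it.

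The 40% and 50% rates are also assumptions, and the fallback one level lower needs at most 1 DLT in 6 (3.3), so clearance on three patients applies to the 10 mg level after 0/3. That stands too.

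A reader might infer three stronger points that the documents do not support:
- **That the MTD is set on a lighter schedule and Cohort 3's schedule is untested.** Days 1-28 are identical, the DLT definition covers the first cycle, and Cohorts 1 and 2 later receive back-to-back cycles. Only the Day 28-to-29 transition differs.
- **That 10 mg is already near the limit, because Table 1-1 shows 14 of 45 patients (31%) with Grade 3 or higher events.** Those are drug-suspected events not confined to cycle 1 or to the 3.3 definition. The dose discussion before section 1.5 cites the same table for a low DLT frequency at 10 mg/d.
- **That a too toxic level would be given to all 32.** This would also need at least one response in 17 and no intervention by the DSMC.

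**Conclusion.** The concern holds as a gap in the statistical design. The Cohort 2 rule passes a 40% level with probability 0.31 and a 50% level with 0.17, or 0.15-0.28 and 0.09-0.16 if Cohort 1 must also pass with an assumed 5 mg rate of 10-30%. These are probabilities given a true rate, not estimates that 10 mg has that rate. Once the dose is cleared, the probability that a pre-set rule stops Cohort 3 for toxicity is zero at any DLT rate, because there is no such rule; stopping depends on DSMC judgement. The protective claim in 10.1 is accurate for inactivity and should not be read as covering toxicity. The results assume independent patients with a common DLT rate.

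**What to change.** Add a short paragraph to 10.1:
- Count section 3.3 DLTs in cycle 1 of each Cohort 3 patient, keeping the protocol's first-cycle window. Count a hematologic event once the three-week recovery criterion in 3.3 can be judged.
- Suspend accrual pending DSMC review at, for example, ≥4 of 6, ≥7 of 12, ≥9 of 17 or ≥12 of 24 patients. Suspension for review is a consequence section 3.2 already uses.
- State the operating characteristics tabulated above, and word the protective claim so that it distinguishes inactivity from toxicity.

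**Cost.** Adverse event forms are already due within 10 days of the end of each cycle (12.1.2), so the main work is a DLT determination per patient. An unneeded suspension would occur in 2% of trials at a true rate of 20%, 11% at 30% and about 14% at 32%, all below the protocol's limit. Power is modest at 40%: 0.35, so about 65% of such trials would not be flagged. Waiting for the recovery criterion means some patients may enrol before a look is complete, so the saving in enrolment is a best case. Other boundaries could serve; what matters is that one is chosen in advance with its properties stated. No dose or patient-management rule changes.

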5.4 IRB Documentation

The following must be on file with the DF/HCC Lead Institution or designee prior to participant registration:

- Approval Letter of the institution's IRB (An Expedited IRB first approval is NOT acceptable)
- IRB approval for all amendments

It is the individual institution's responsibility to notify its IRB of protocol revisions. Participating institutions will have 90 days from receipt to provide the DH/HCC Lead Institution or designee their IRB approval for Major Amendments* to a protocol.

* **DF/HCC defines a Major Amendment** as: A substantive change in the study which may increase or decrease the risk to study participants. Major revisions require full IRB approval. The following criteria are examples of revisions to a protocol that are considered to be major amendments:

- Change of eligibility (inclusion/exclusion) criteria
- Change in design of protocol
- Change in statistical section
- Change in sample size/accrual (e.g., doubling the sample size)
- Change in informed consent
- Change of estimated dropout rate
- Change of treatment or intervention
- Change of device
- Change in primary objective evaluation process

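### The two-stage rule as written has a type I error of 0.20, not the stated 0.18, and 32 serves both as the number counted and as the accrual goal after an ineligibility allowance

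*Combined protocol and SAP*

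**What the plan says.** Section 10.1 defines the rule in numbered steps. Stage one: "In the first stage, 17 patients will be treated". The stopping rule follows: "If there are 0 responses, the study will be terminated". With at least one response, "the study will proceed to the second stage, accruing an additional 15 patients to a total of 32". Three or more responses in total lead to a recommendation for further study; two or fewer do not. The uninteresting response rate is 5% and the interesting rate is 20%.

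The section gives four operating characteristics. The probability of stopping after 17 patients is put at 0.42 if the true rate is 5% and at 0.02 if it is 20%. Then: "The study will have overall power of 0.95, and overall type I error of 0.18".

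The next sentence reads: "Allowing for a 5% rate of ineligibility, the overall accrual goal will be 32 patients". Section 3.2.3 repeats the number: "The third patient cohort will consist of 32 patients".

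Section 10.2 plans a response rate with a 95% confidence interval and does not name the denominator.

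**The concern.** Two things do not fit together.

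First, the stated type I error does not follow from the stated rule. This figure is the chance of recommending a regimen that the investigators themselves regard as not worth pursuing. It is already lenient. Under the rule as written it is one in five, and those approving the plan were told 0.18.

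Second, 32 has two roles. It is the total on which the decision is made, and it is also the accrual goal after an allowance for ineligible patients. An allowance makes sense only if the number counted is smaller than the number accrued. The plan does not say whether a treated patient later found ineligible counts. With exactly 3 responses, one of them in such a patient, the conclusion would depend on a choice made after the data are known.

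**Working it through.** **Inputs, all from Section 10.1.** First stage n1 = 17; stop at 0 responses; second stage n2 = 15; success at 3 or more responses in total; p = 0.05 (null) and p = 0.20 (alternative).

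**Early stopping.** P(stop) = (1 − p)^17.
- p = 0.05: 0.95^17 = 0.418 (stated 0.42, reproduces).
- p = 0.20: 0.80^17 = 0.0225 (stated 0.02, reproduces).

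**Probability of a positive conclusion.** With X1 ~ Bin(17, p) and X2 ~ Bin(n2, p),

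P(go) = P(X1 = 1)·P(X2 ≥ 2) + P(X1 = 2)·P(X2 ≥ 1) + P(X1 ≥ 3).

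For n2 = 15:
- p = 0.20: 0.0957 × 0.8329 + 0.1914 × 0.9648 + 0.6904 = 0.0797 + 0.1847 + 0.6904 = 0.9548 (stated 0.95, reproduces).
- p = 0.05: 0.3741 × 0.1710 + 0.1575 × 0.5367 + 0.0503 = 0.0640 + 0.0845 + 0.0503 = 0.1987 with unrounded terms (stated 0.18, **does not reproduce**).

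A simulation of 4 million trials gave 0.1987 and 0.9547.

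**Can another reading give 0.18 at 32 patients?** A single stage of 32 gives 0.214; a Poisson approximation 0.199; success at 4 or more 0.072; stopping at 1 or fewer 0.135. None does.

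**Can the ineligibility allowance explain it?** 32 × 0.95 = 30.4, so about 30 eligible; in reverse, 30/0.95 = 31.6, which rounds up to 32. Keeping 17 in the first stage and varying the second:

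| Patients counted | Type I error (p = 0.05) | Power (p = 0.20) |
|---|---|---|
| 17 + 15 = 32 | 0.1987 | 0.9548 |
| 17 + 14 = 31 | 0.1882 | 0.9501 |
| 17 + 13 = 30 | 0.1776 | 0.9446 |
| 17 + 12 = 29 | 0.1669 | 0.9380 |

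At 30 the type I error rounds to 0.18, but power rounds to 0.94. For second stages from 8 to 19, the type I error rounds to 0.18 only at 13, and power rounds to 0.95 only at 14 and 15. No second stage gives both stated figures.

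The first stage cannot be moved either. The stated 0.42 fixes it at 17, since 0.95^16 = 0.440 and 0.95^18 = 0.397.

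**Ineligible patients kept in the denominator as non-responders.** Suppose all 32 are counted but each is ineligible with probability 5% and cannot be scored a responder. The effective rates are 0.05 × 0.95 = 0.0475 and 0.20 × 0.95 = 0.19. The 17 + 15 rule then gives 0.179 and 0.942, and early stopping at a 20% response rate rises from 0.023 to 0.028. Again the type I error rounds to 0.18 and the power to 0.94.

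**How often would the counting question arise?** At 5% ineligibility, the chance that all 32 are eligible is 0.95^32 = 0.194. The chance of at least 30 eligible is 0.786.

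**The case against.** The strongest reply is that Section 10.1 nearly explains itself. The sentence after the 0.18 mentions the 5% allowance, 32 × 0.95 is about 30, and a 17 + 13 design gives 0.178. On this view the design was computed on 30 eligible patients and the inflated number was then written into the rule, so the fault is one of drafting. Power misses its stated value by only about half a point. This is a plausible origin, but the plan does not say it. The numbered steps say 15 and 32 and refer to treated patients, and the 30-patient reading still does not give a power of 0.95 to two decimals.

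A second reply is that ineligible patients should be rare, because the registrar checks eligibility before treatment (Section 11.2). That is fair, but the plan itself allows for 5%, and at that rate all 32 are eligible in only about one trial in five.

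A third reply is that counting ineligible patients reverses the apparent purpose of the allowance and removes the only buffer, since Section 11.1 foresees registered patients who never start therapy. This stands in part: a team that meant to analyse eligible patients may prefer to define the rule on them, and either version should say what happens if the planned number is not reached.

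The reply that the numerical effect is small also stands. It limits the weight of the point but does not make the stated figure right.

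**Conclusion.** The stated type I error is wrong for the rule as written: 0.199 against 0.18, a gap of about two percentage points that is not rounding. The other three operating characteristics reproduce. If only about 30 eligible patients are meant to count, 0.18 is right but the stated power is not (0.945, so 0.94 to two decimals), and the rule names the wrong numbers. Either way one sentence in Section 10.1 must change, and the handling of treated but ineligible patients must be stated.

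The result rests on exact binomial probabilities with independent patients and a common response rate, using only numbers printed in Section 10.1. The decision boundaries and the planned estimate with its 95% confidence interval are not affected. The point should be fixed, but it does not threaten the design.

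**What to change.** **Simplest change.** Keep the rule on all 32 treated patients. In Section 10.1, state power 0.95 and type I error 0.20. Replace the ineligibility sentence with one such as: *Every treated Cohort 3 patient, including any later found ineligible, is counted at both looks (17 and 32) with the confirmed response observed.* It is worth adding whether registered patients who never start treatment are replaced. If one is not and 31 are counted, the figures are 0.188 and 0.950.

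**Alternative.** Define the rule on eligible patients: first look after 17 eligible (about 18 accrued, 17/0.95 = 17.9), then 13 more to 30 eligible, success at 3 or more responses, accrual up to 32 (30/0.95 = 31.6). State type I error 0.18 and power 0.94. Because 32 accrued patients yield at least 30 eligible with probability only 0.79 at 5% ineligibility, this version must also say what applies below 30.

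**Cost.** The simplest change takes two sentences and alters no boundary or patient number; one stated figure becomes slightly less favourable. Appendix B, Section 5.4 lists "Change in statistical section" among its examples of major amendments, which need full IRB approval, so the correction is best bundled with another amendment.
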